8.2.3 Suspected Unexpected Serious Adverse Reactions

An SAE that is also an unexpected adverse drug reaction is called a suspected unexpected serious adverse reaction (SUSAR). Unexpected adverse reactions are adverse reactions of which the nature or severity is not consistent with the applicable product information (*ie, the most recent version of the IB for GBT021601* e.g., IB for an unapproved investigational medicinal product).

The Sponsor or its representative (eg, ICON if agreed to before start of the study) will promptly report (expedited reporting) the following SUSARs to the IEC:

- SUSARs that have arisen in the current clinical study that was assessed by the IEC.
- SUSARs that have arisen in other clinical studies of the same Sponsor and with the same medicinal product, and that could have consequences for the safety of the participants involved in the current clinical study that was assessed by the IEC.

The Sponsor or designee will promptly report (expedited reporting) all SUSARs to the CA and the Medicine Evaluation Board of the country where this study is conducted and to the CAs in other Member States, as applicable. The Sponsor or designee will inform regulatory authorities, IECs, and Investigators, as applicable, of any events (eg, change to the safety profile of GBT021601, major safety findings that may place study participants at risk) that may occur during the clinical study that do not fall within the definition of a SUSAR but may adversely affect the safety of study participants.

SUSARs that have already been reported to the EMA Eudravigilance database do not have to be reported again to the CA and the Medicine Evaluation Board because they have direct access to the Eudravigilance database.

Expedited reporting will occur no later than 15 calendar days after the Sponsor or its representative has first knowledge of the adverse reactions. For fatal or life-threatening cases, the term will be maximally 7 calendar days for a preliminary report with another 8 calendar days for completion of the report.

8.2.4 Follow-up of Adverse Events

Follow-up of AEs will continue until resolution, stabilization, or death. In case of ongoing AEs at database lock, the data obtained at database closure will be used in the statistical analysis. The follow-up of the AE will be documented in the source documents and will be described in the final CSR only if considered relevant by the Investigator.

8.3 Pregnancy

A female clinical study participant should not be dosed and must be instructed to inform the Investigator immediately if she becomes pregnant during the study. Pregnancies occurring up to 140 days after dosing or up to the last 24-hour visit (if collection of blood and excretion is continued after this 140-day period) must also be reported to the Investigator or designee. The Investigator will make arrangements for the participant to be counseled by a specialist, to discuss the risks of continuing with the pregnancy and the possible effects on the fetus. Monitoring of the participant should continue until the outcome of the pregnancy is known and the child will also be followed for 3 months after delivery.

The Investigator should report all pregnancies of female clinical study participants to the Sponsor within 24 hours of becoming aware of them.

If the Investigator becomes aware of a pregnancy occurring in the partner of a male participant participating in the study up to 140 days after dosing or up to the last 24-hour visit (if collection of blood and excretion is continued after this 140-day period) of the male participant, the pregnancy should be reported to the Sponsor or designee within 24 hours. The Investigator may make arrangements for the partner to be counseled by a specialist, to discuss the risks of continuing with the pregnancy and the possible effects on the fetus. Monitoring of the partner should continue until the outcome of the pregnancy is known and the child will also be followed for 3 months after delivery.

Appendix 4: Shells for Post-Text Tables, Figures and Listings	
19.0 Document History	

3.0 Introduction

This Statistical Analysis Plan (SAP) describes the statistical methods that will be used during the analysis and reporting of data collected under Global Blood Therapeutics (GBT), Inc., Protocol GBT021601-013.

This SAP should be read in conjunction with the clinical study protocol and electronic case report form (eCRF). This version of the plan has been developed using the protocol Version 3.0, dated 13-Mar-2023 (including all amendments up to this protocol date) and the final eCRF(s) dated 31-Oct-2022.

An approved and signed SAP is a requirement for database lock.

This SAP only covers the results that will be processed by the ICON Early Development Services (EDS) Biostatistics Department, Statistical Programming Department and Pharmacokinetic Department.

ICON EDS will perform the pharmacokinetic (PK), and safety and tolerability evaluation.

Metabolic profiling is not described in this SAP and will not be included in the corresponding TFLs. This SAP supersedes the statistical considerations identified in the protocol; where considerations are substantially different, they will be so identified. Any post-hoc or unplanned analyses, or significant changes from the planned analysis in this SAP performed to provide results for inclusion in the clinical study report (CSR) but not included in this SAP, will be clearly identified in Section 9.8.2 of the CSR. Changes to planned analyses do not require an updated SAP but should be included in the CSR if significant.

4.0 Changes from Previous Version of Approved SAP

This is the first version of the SAP.

5.0 Study Objectives

5.1 Primary

- To determine the whole blood and plasma concentrations of ¹⁴C-GBT021601 total radioactivity.
- To assess the mass balance by determining ¹⁴C-GBT021601 total radioactivity excreted in urine and feces.
- To determine the PK of GBT021601 in whole blood, plasma, and urine.

5.1.1 Primary Endpoint

- Concentrations of GBT021601 and of ¹⁴C-GBT021601 total radioactivity in whole blood and plasma
- Amount and fraction of ¹⁴C-GBT021601 total radioactivity dose excreted in urine, feces, emesis (if produced).
- PK parameters of GBT021601 and ¹⁴C-GBT021601 total radioactivity, as feasible, in whole blood and plasma (AUC₀₋₂₄, AUC_{0-last}, AUC_{0-inf}, C_{max}, T_{max}, T_{1/2}, CL_R, CL/F, and V_z/F, if possible, and any other PK parameters as appropriate).
- Distribution of ¹⁴C- GBT021601 total radioactivity in urine and feces.

5.2 Secondary

- To assess the safety and tolerability of GBT021601 administration in healthy participants.
- To characterize and identify metabolites of ¹⁴C-GBT021601 in whole blood, plasma, urine, and feces.

5.2.1 Secondary Endpoint

- Incidence and severity of adverse events (AEs).
- Other safety results: clinical laboratory results, vital signs, 12-lead electrocardiogram (ECG) and physical examinations.

EDSREP 009 T 01 G Page 4 of 30

Metabolite profiling is not covered in this SAP.

6.0 Study Design

This Phase 1, single-center, open-label study will be conducted to evaluate the absorption, distribution, metabolism, and excretion (ADME) of GBT021601 in 8 to 10 healthy male or female participants. GBT021601 will be administered as a single oral dose of 200 mg GBT021601, containing ~74 kBq (~2 μ Ci) of ¹⁴C-GBT021601, under fasted conditions.

After dosing on Day 1, blood (whole blood and plasma) and excreta (urine and feces) will be collected for up to 7 months due to the long elimination half-life from blood and plasma (approximately 28 to 30 days) of GBT021601, depending on how much radioactivity is recovered in excreta and the rate of elimination of radioactivity. Vomitus will be collected, if possible, if a participant vomits within 24 hours after study drug administration. Participants will remain confined in the clinical research unit (CRU) until discharge on Day 29. After discharge from the CRU, participants will return to the CRU for up to 11 visits. Each follow-up visit to collect blood and excreta will be a 24-hour stay in the CRU.

Concentrations of total radioactivity excreta will be assayed on a periodic basis to enable the Sponsor/Investigator to determine how long samples should be collected. Criteria for ending the collection of blood and excreta in a participant after Day 29 are: 1) ≥90% of the administered radioactive dose is recovered in excreta collected to date, or 2) radioactivity is undetectable in urine and feces during 2 consecutive 24-hour collection periods, or 3) until the end-of-study (EoS) visit on Day 206.

Participants will receive the appropriate containers to collect all feces at home within 24 hours prior to admission on Day -1 and each of the 24-hour stays. This sample will be used if no feces is produced between admission on Day -1 and dosing (as blank sample) or during the 24-hour stays after Day 29, respectively.

The total duration of study participation from screening until EoS visit will be up to approximately 234 days. For an overview of the study design, see Table 1.

Table 1 Schematic Study Design

EDSREP 009 T 01 G Page 5 of 30

Statistical Analysis Plan GBT2180A-2180AX Protocol: GBT021601-013

Version Date: 01-May-2023

Visit	Screening	Long-term confinement in CRU		nement in CRU	24-hour visits (up to 11 visits) a
Activity				Assessments/	PK sampling
	Eligibility	Admission	Dosing	PK sampling	(collection of blood and excreta)
Study Day(s)	-28 to -2	Day -1	Day 1	Days 1 to 29 (ie,	35-36 (±1 day),
				discharge)	42-43 (±1 day),
					56-57(±2 days),
					70-71 (±2 days),
					84-85 (±2 days),
					98-99 (±2 days),
					112-113 (±2 days),
					136-137 (±2 days),
					150-151 (±2 days),
					178-179 (±2 days),
					206-207 (±2 days; EoS/ET)

CRU=clinical research unit; EoS=end of study; PK=pharmacokinetic(s)

a. Criteria for ending the collection of blood and excreta in a participant after Day 29 are: 1) ≥90% of the administered radioactive dose is recovered in excreta collected to date, or 2) radioactivity is undetectable in urine and feces during 2 consecutive 24-hour collection periods, or 3) until the EoS visit on Day 206. If these criteria are met after Day 29 and before Day 206, participants will return to the CRU for EoS assessments at a separate visit 7 (±3) days after the last 24-hour visit.

6.1 Sample Size Considerations

No formal sample size calculation was made. Based on similar studies, the sample size of 8-10 participants was considered appropriate for this Phase 1 ADME study.

7.0 Overview of Planned Analysis

7.1 Changes from Protocol

The % Hb occupancy (at C_{max}) was added as a PK parameter.

The protocol states "Concentrations of total radioactivity in blood and excreta will be assayed weekly during the 30-day confinement phase and thereafter within 3 days of the 24-hour collections." However, blood and plasma will not be assayed weekly for concentrations of total radioactivity during the 30-day confinement phase. Only excreta will be assayed weekly for total radioactivity during the 30-day confinement phase, as described in the Protocol Clarification Memo dated 27-Oct-2022.

The definition of treatment emergent adverse events (TEAEs) has been updated compared to the protocol. TEAE are those which occur (or worsen) after the dose of study drug, consistent with the protocol text. Additionally, AEs need to take place during the on-treatment period, defined as the period after the dose of study drug and before the minimum of (Study Day 56, study discontinuation), to be considered as TEAEs. Day 56 has been chosen for this purpose based on the half-life of GBT021601.

7.2 Planned interim Analysis and Key Results

There are no interim analyses planned for this study.

7.3 Final Analysis

The final TFLs will be created after all participants have completed the end of study (EOS) visit or have discontinued the study.

EDSREP 009 T 01 G Page 6 of 30

8.0 Data Review

8.1 Data Management

Data handling and transfer will take place under the ICON Data Management Plan for the study.

8.2 Acceptance of Data for Summarization

Programming of analysis datasets and TFLs may be ongoing during the data management of the study. However, programming of analysis datasets and TFLs will be completed and quality controlled (QC'd) after database lock. The draft safety TFLs will also be QC'd before database lock. Only quality assured (QA'd) results released by the Safety Laboratory, Bioanalytical Laboratory, or other external data source will be used for the programming of analysis datasets and TFLs for the final report. Any data values requiring investigation or corrections that are identified while programming the analysis datasets and TFLs will be sent to the project Data Manager for resolution. If the issue affects the TFLs the Programmer or Statistician who identified the issue will follow it to resolution.

9.0 Definitions and General Analysis Methods

9.1 Analysis Data Presentation

9.1.1 Rounding

In listings, data will be presented with the same precision as the original data. Derived data will be rounded for presentation purposes.

For all summaries, the mean and median will be presented to one decimal place greater than the data, standard deviation to 2 greater than the data, and the minimum (min) and maximum (max) will be presented to the same number of decimal places as the data. Frequency percentages will be presented with one decimal. Individual values and descriptive statistics of PK concentrations in all matrices (e.g. whole blood, plasma) and parameters will generally be presented with 3 decimals, except t_{max} (which will be reported with 2 decimals). Values greater than 999 will be presented as integers. The coefficients of variation (CVs) as a percentage will be presented to 1 decimal place.

9.1.2 Imputation

[figure not shown]
Unless otherwise noted, data will not be imputed. Imputation will only be used for:

- PK concentrations below the quantifiable limit (BQL) (see Section 16.1.2).
- PK amounts excreted will be interpolated between confinement and 24 hour visits and between subsequent 24 hour visits (see Section 16.1.2)
- Missing start or end date/times of AEs for the calculation of onset and duration (see Section 17.1.1).
- Missing adverse event (AE) severity, relationship and seriousness of AEs see Section 17.1.1).
- Safety laboratory data that are <x or >x (e.g. "<1.03", ">1000"): the analysis value or normal limit value will be the value of the detection limit itself plus or minus one precision unit for the parameter concerned (respectively 1.02 and 1001 in the example). The values before imputation ("<1.03", ">1000") will only be shown in listings. Listings will present the values before imputation.

9.1.3 Descriptive Statistics

Unless otherwise indicated, continuous variables will be summarized with the following descriptive statistics: n (number of observations), (arithmetic) mean, standard deviation (SD), min value, median, and max value. For the summary statistics for PK, see Section 16.2.1 for PK concentrations and Section 16.2.3 for PK parameters.

EDSREP 009 T 01 G Page 7 of 30

Categorical data will be summarized with frequencies and percentages. Percentages by categories will be based on the number of participants exposed.

For categorical data, the categories will be presented in the tables exactly as they appear in the CRF / Database.

9.1.4 Pooling

Data will not be pooled.

9.1.5 Unscheduled Measurements

Unscheduled measurements will be included in the listings. With the exception of unscheduled measurements used for baseline, unscheduled measurements will be excluded from the descriptive statistics and statistical analysis.

9.2 Analysis Data Definitions

9.2.1 Baseline Definition

Unless otherwise stated, baseline for postdose evaluations is defined as the last observation recorded before study drug administration. The last observation can be an unscheduled measurement, in which case the baseline can be an unscheduled measurement.

9.2.2 Treatment/Participant Grouping

Label	Grouping
Study Drug	GBT021601 + ¹⁴ C-GBT021601
Treatment/Dose Level	200 mg GBT021601 + ~74 kBq (~2 μCi) ¹⁴ C-GBT021601

9.2.3 Common Variable Derivations

Variable	Data Type	Definition/Calculation
Change from Baseline	All	Postdose Observation minus Baseline Observation
Analysis Study Day (Prior to Dose)	All	Date of Measurement minus Dose Date
Analysis Study Day (Post Dose)	All	Date of Measurement minus Dose Date +1
Day 1	All	Day 1 starts at date/time of dosing

9.2.4 ADaM Datasets and Metadata

The analysis datasets will be generated in accordance with Clinical Data Interchange Standard Consortium (CDISC) Analysis Data Model (ADaM) Version 2.1. The ADaM datasets in Table 2 ADaM Datasets will be created, with independent production and validation programming, per ICONs SOP. Additional ADaMs may be created, if needed for TFL programming.

Table 2 ADaM Datasets

ADaM Dataset Name	Description
ADSL	Subject-Level Analysis Dataset
ADAE	Adverse Events Analysis Dataset

FDSRFP 009 T 01 G Page 8 of 30

ADaM Dataset Name	Description
ADEG	ECG Analysis Dataset
ADLB	Laboratory Test Results Analysis Dataset
ADPC	Pharmacokinetic Concentrations Analysis Dataset
ADPP	Pharmacokinetic Parameters Analysis Dataset
ADVS	Vital Signs Analysis Dataset

ADaM compliant datasets will be delivered to the sponsor. A define.xml file version 2 with the corresponding metadata will be included.

9.3 Software

The statistical analysis and reporting will be done using SAS® for Windows™ Version 9.4 or higher (SAS Institute, Inc.).

PK parameter calculations will primarily be done using Phoenix® WinNonlin® (WNL) Version 8.3.4.295 or higher (Certara USA Inc.). Additional PK computations may be performed in SAS®.

9.4 Statistical Methods

9.4.1 Statistical Outlier Determination

No statistical outlier analysis is planned.

9.4.2 Predetermined Covariates and Prognostic Factors

There are no predetermined covariates or prognostic factors.

9.4.3 Hypothesis Testing

No formal hypothesis testing will be done.

9.5 TFL Layout

Report layout will be according to the ICON EDS – International Conference on Harmonization (ICH) E3 compliant – CSR Template. The layout of TFLs will be according to the ICON EDS standards.

Table shells will be provided as separate document to this SAP. Small changes to TFL layout compared to the shell layout, due to the nature of the data may be required after database lock at the discretion of the ICON project statistician.

The TFLs will be provided in rtf format (one file for the Participant Data Listings, and one for the Table and Figures) referred to, but not included in text.

Format:

- Data in listings will be sorted by participant number and time point.
- Data in tables will be sorted by time point.
- Column titles will be in title case letters.
 - All tables and listings will be in landscape format with minimum of 1 inch margin at the top, 3/4" edge margin at the bottom and 1/2" for other margins. All figures will be in portrait format, with the exception of the combined individual plots, which will be in landscape format.
- Courier New of no less than 8-point will be used for tables and listings.
- The treatment labels will be as outlined in Section 9.2.2.

EDSREP 009 T 01 G Page 9 of 30

10.0 Analysis Sets

Table 3 Analysis Sets

Analyses	Enrolled Set	Safety Set	Pharmacokinetic Set
Disposition Summaries	✓		
Safety Assessments		✓	
Baseline Characteristics		✓	
PK Concentrations		√a	√b
PK Parameters			✓

a: For PK concentration listings. b: For PK concentration summaries.

10.1 Enrolled Set

The enrolled set will consist of all subjects that signed the Informed Consent Form. This set will be used for disposition summaries.

10.2 Safety Set

All participants who have received 1 dose of GBT021601. This set will be used for the safety data summaries, baseline characteristic summaries and PK concentration listings.

10 3 Pharmacokinetic Set

All participants who have received 1 dose of GBT021601 and provided at least 1 measurable postdose PK concentration of GBT021601 or total radioactivity in whole blood or plasma. This set will be used for PK concentrations and PK parameter summaries.

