16.1.2.2 Pharmacokinetic Amounts Excreted

Urinary and fecal PK parameters will be calculated using SAS and/or WNL. Excretions in mg equivalent (mg eq) for each interval (Ae_{t1-t2}) will be derived from the urinary and fecal concentrations and the sample collection interval volumes or weights respectively, by multiplying the concentration in the interval (C) and the volume or weight (V):

$$Ae_{t1-t2} = C \times V$$

If the concentration is < lower limit of quantification (LLOQ), the excretion will be assumed to be zero. For intervals in which no sample was collected (e.g., no defecation), the excretion will be assumed to be zero.

Cumulative excretions for each continuously sampled interval will be calculated by adding the excretions in the current and all previous collection intervals:

$$Ae_{0-t} = \sum_{i=1}^{n} \left(Ae_{t_{start} - t_{end}} \right)_{i}$$

The excretion rate ($\Delta Ae/\Delta t$) will also be calculated by dividing the excretion in each interval by the time difference in hours between the end and the start of the collection interval:

$$\frac{\Delta Ae}{\Delta t} = \frac{Ae}{t_{end} - t_{start}}$$

If a participant has not met the criteria for ending the collection of blood and excreta on Day 29 (i.e., end of confinement), cumulative excretion will be calculated up to and including the last continuous 24 hour visit during confinement. Interpolation will be used to estimate urinary and fecal excretion between confinement and 24 hour visits and between subsequent 24 hour visits, the midpoint method will be used to estimate Ae t_{start-tend}. The excretion rate of each collection interval will be plotted as a function of the midpoint of the respective interval. The area under this curve is Ae.

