16.1.2.3 Excretion Parameters

• PK Parameters for GBT021601 and ¹⁴C-GBT021601 total radioactivity as defined in Table 5.

EDSREP 009 T 01 G Page 15 of 30

Table 5 PK parameters for excretion

Parameter	Description	Analyte
CLR	Renal clearance	GBT021601
Ae _{urine}	Cumulative amount of drug excreted in urine at each interval	¹⁴ C-GBT021601 Total Radioactivity, GBT021601
fe _{urine}	Fraction of the dose administered excreted in urine (%) at each interval	¹⁴ C-GBT021601 Total Radioactivity, GBT021601
Ae _{feces}	Cumulative amount of drug excreted in feces at each interval	¹⁴ C-GBT021601 Total Radioactivity
fe _{feces}	Fraction of the dose administered excreted in feces (%) at each interval	¹⁴ C-GBT021601 Total Radioactivity
Ae _{vomit}	Cumulative amount of drug excreted in vomitus (if applicable)	¹⁴ C-GBT021601 Total Radioactivity
fe _{vomit}	Fraction of the dose administered excreted in vomitus (%), if produced	¹⁴ C-GBT021601 Total Radioactivity
Ae _{total}	Total amount of drug excreted in urine and feces	¹⁴ C-GBT021601 Total Radioactivity
fe _{total}	Total fraction of the dose administered excreted in urine and feces	¹⁴ C-GBT021601 Total Radioactivity

The administered dose is calculated by multiplying the amount (400 mL) of the solution given by the radioactivity per mL of the solution.

The radioactivity per mL solution is calculated by multiplying the label claim (0.185 kBq/mL) by the % radioactivity results (98.5%) of the product (which is established by the QC department):

Administered dose =
$$400 \text{ mL} * 0.185 (kBq/mL) * 0.985 = 72.89 kBq$$

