16.2.3 Pharmacokinetic Parameters

PK parameters will be estimated using non-compartmental methods with WinNonlin® and additional computations may be performed in SAS.

The whole blood, plasma and CCI for GBT021601 and ¹⁴C-GBT021601 Total Radioactivity will be estimated from the concentration-time profiles. In estimating the PK parameters, BQL values at the beginning of the profile will be set to zero. BQL values that occur after the first quantifiable point will be considered missing. Values that are embedded between BQLs, or quantifiable values occurring after 2 or more BQLs, will be set to missing at the discretion of the pharmacokineticist. All concentration values reported as no results (not collected or not determined (ND)) values will be treated as missing. Actual sampling times, rather than scheduled sampling times, will be used in all computations involving sampling times.

Descriptive statistics (number of participants, mean, geometric mean, standard deviation, coefficient of variation, geometric coefficient of variation, median, minimum, and maximum) will be used to summarize the calculated PK parameters for GBT021601 and Total Radioactivity. For 14 C-GBT021601 Individual plasma PK parameters will be presented together with descriptive statistics. For t_{max} , only median, min and max will be presented.

Only data points that describe the terminal elimination log-linear decline will be used in the regression equation for calculation of λ_z ; C_{max} and any data point in the distribution phase are not included in the calculation. A minimum of 3 points will be used for determination of K_{el} . A general rule of adjusted $R^2 \geq 0.80$ will be considered as acceptable for calculation of K_{el} . If adjusted R^2 falls below 0.80, then λ_z will be reported as Not Determined (ND) and that participant's K_{el} , $t_{1/2}$, CL/F, V_z/F and $AUC_{0-\text{inf}}$ will be reported in the appropriate listings but will be flagged and excluded from descriptive summaries and statistical analysis.

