Table 14.2.2.2	Individual Values and Descriptive Statistics of Amounts of Total ¹⁴ C-GBT021601 Radioactivity Excreted in Urine, Feces and Total by Interval	PK
Table 14.2.2.3	Individual Values and Descriptive Statistics of GBT021601 Excretion Parameters in Urine	PK
Table 14.2.2.4	Individual Values and Descriptive Statistics of Total ¹⁴ C-GBT021601 Radioactivity Excretion Parameters in Urine, Feces and Total Recovery	PK
Figure 14.2.2.5	Arithmetic Mean Cumulative ¹⁴ C-GBT021601 Recovery in Urine, Feces and Total Versus Time	PK
Figure 14.2.2.6	Individual Cumulative ¹⁴ C-GBT021601 Recovery in Urine, Feces and Total Versus Time	PK
Section 14.3 – Safety Data		

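### Total recovery is summarised over a PK set with no excreta condition, so a participant who withdraws early enters the mean with a truncated value

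*SAP*

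**What the plan says.** Mass balance is a primary objective (Protocol 2.1, SAP 5.1), and the amount and fraction of the radioactive dose excreted is a primary endpoint (SAP 5.1.1).

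- **Population.** Besides one dose, the PK set requires only that the participant "provided at least 1 measurable postdose PK concentration of GBT021601 or total radioactivity in whole blood or plasma" (SAP 10.3; same condition in Protocol 3.6.1.2). The SAP adds: "This set will be used for PK concentrations and PK parameter summaries".
- **Endpoint and output.** SAP Table 5 defines fe_total as "Total fraction of the dose administered excreted in urine and feces". Table 14.2.2.4, which covers "Radioactivity Excretion Parameters in Urine, Feces and Total Recovery", is assigned to the PK set (SAP Appendix 3).
- **Calculation.** SAP 16.1.2.2 adds up the collected intervals and counts an interval without a sample as zero. For the gaps after confinement, "Interpolation will be used to estimate urinary and fecal excretion between confinement and 24 hour visits and between subsequent 24 hour visits". It has no step beyond a participant's last collection.
- **End of collection.** Criterion 1 is "≥90% of the administered radioactive dose is recovered in excreta collected to date". Criterion 2 is undetectable radioactivity in urine and feces over two consecutive 24-hour collections. Otherwise collection runs to Day 206 (SAP 6.0).
- **Exclusions.** Parameters that "will be flagged and excluded from descriptive summaries and statistical analysis" are those depending on the terminal slope (SAP 16.2.3). The pharmacokineticist's discretion in Protocol 3.6.2.1 covers anomalous concentrations. Neither reaches Ae or fe.
- **Withdrawal.** Protocol 3.6.3 allows for dropout over the long study. Under Protocol 3.3.4 a drug-related withdrawal is not replaced and any other may be. Nothing removes a replaced participant from the PK set.
- **Statistics.** PK parameters are summarised by "number of participants, mean, geometric mean, standard deviation, coefficient of variation, geometric coefficient of variation, median, minimum, and maximum" (SAP 16.2.3). SAP 16.2.4 lists a similar set for amounts excreted, by interval.

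**The concern.** Membership of the PK set is settled by a blood or plasma sample, while total recovery depends on months of urine and feces. Someone who leaves on Day 2 with one measurable concentration counts in mean total recovery exactly as someone followed to Day 206 does.

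The mean of fe_total is the headline figure for a primary objective. If it falls because a participant left, a reader may take incomplete follow-up for incomplete elimination. With 8 to 10 participants, each carries 10% to 12.5% of the mean.

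A related gap is that the zero rule for uncollected intervals gives a missed bowel movement as its example and does not mention withdrawal. It is unclear whether intervals after withdrawal enter the by-interval summaries as zero or as missing.

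**Working it through.** **The plan's own figure.** The denominator of fe_total (SAP 16.1.2.3) is 400 mL × 0.185 kBq/mL × 0.985 = 72.89 kBq. It reproduces. The sample size has no calculation to reproduce.

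**Direction.** Cumulative excretion is a sum of non-negative amounts, so recovery at withdrawal, r, cannot exceed what the same person would have reached at an ending criterion. If all others finish at C, and the withdrawn participant would have too, one withdrawal among n lowers the mean by (C − r)/n.

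**Inputs.** n = 8 or 10 (Protocol 3.1.1). The half-life of 28 to 30 days (SAP 6.0) is for parent drug in blood and plasma; applying its midpoint, T = 29, to excretion of total radioactivity is an assumption. So are the plateau F = 95% and the withdrawal days.

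**Model.** r(d) = 95 × (1 − 2^(−(d−1)/29)). It reaches 90% at d = 1 + 29 × log2(95/5) = 124.2, so criterion 1 is first met at the Day 136 visit and C = 91.23. This counts interpolated amounts toward criterion 1.

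| Withdrawal day | r (%) | Mean shortfall, n=8 | Mean shortfall, n=10 | Geometric mean shortfall, n=8 |
|---|---|---|---|---|
| 14 | 25.4 | 8.2 | 6.6 | 13.5 |
| 29 | 46.4 | 5.6 | 4.5 | 7.4 |
| 56 | 69.5 | 2.7 | 2.2 | 3.1 |
| 70 | 76.7 | 1.8 | 1.4 | 2.0 |
| 112 | 88.3 | 0.4 | 0.3 | 0.4 |

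Example, Day 56, n = 8: (91.23 − 69.48)/8 = 2.7. The geometric mean shortfall is C − C × (r/C)^(1/n). If an unreplaced eight is instead eight completers plus one replaced withdrawal (n = 9), the mean falls by 7.3, 5.0, 2.4, 1.6 or 0.3.

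**SD.** With an assumed completer SD s = 3, the expected variance is [(n−2)s² + ((n−1)/n)((C−r)² + s²/(n−1))]/(n−1). At n = 8 the SD is about 23, 16, 8, 6 and 3 for the five days. The last is essentially unchanged.

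**Other reading of criterion 1.** If only physically collected amounts count, the model gives 46.4% by Day 29 plus about 3.8% from the eleven 24-hour stays, about 50% in all. Criterion 1 is then never met and completers run to the Day 206–207 stay, where the model with interpolation gives C = 94.31. The n = 8 shortfalls become 8.6, 6.0, 3.1, 2.2 and 0.8.

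**Sensitivity (n = 8; Days 14, 29, 56, 70, 112).**
- T = 28 or 30: each shortfall changes by at most 0.1.
- 30% lost early in feces, r = 30 + 65 × (1 − 2^(−(d−1)/29)), C = 90.4 at Day 112: 5.4, 3.6, 1.6, 1.0, 0.
- Plateau 80%, collection to Day 206, C = 79.4: 7.3, 5.0, 2.6, 1.8, 0.6.

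**Would a completer summary be unbiased?** Take n = 8, seven completers at 91.23 and one withdrawal at Day 56.
- Low excreter (plateau 75%, T = 29; 54.9 at Day 56, 74.4 at Day 206): full follow-up (7 × 91.23 + 74.4)/8 = 89.1; PK set (7 × 91.23 + 54.9)/8 = 86.7; completers 91.2. The two summaries bracket the full-follow-up mean.
- Fast excreter (plateau 98%, T = 24; 78.0 at Day 56, first above 90% at the Day 98 visit with 92.05): full follow-up (7 × 91.23 + 92.05)/8 = 91.3; PK set (7 × 91.23 + 78.0)/8 = 89.6; completers 91.2. Both summaries lie below it.

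**The case against.** Keeping every dosed participant with a measurable concentration is a defensible all-treated choice in a study without hypothesis tests (SAP 9.4.3). A reader might infer that the PK set definition is an error; the documents do not support that, because the definition is consistent across both and contradicts nothing.

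The truncation will also be visible. Individual values stand beside the statistics in Table 14.2.2.4. Median, minimum and maximum are planned, amounts are summarised by interval with n (SAP 16.2.4), individual cumulative curves and an excretion listing are produced, and withdrawal reasons are tabulated (SAP 11.0). Protocol 3.7 requires missing data to be explained in the study report. With ten rows or fewer, a reader could recompute the mean. All of this stands and limits the harm, but none of it alters the planned mean, geometric mean or SD. Leaving the choice to the report means making it once recoveries are known.

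SAP 16.1.2.2 also gives a cumulative value to the end of confinement, on which anyone leaving after Day 29 is comparable with the rest. That helps for later withdrawals only, and the same section then carries excretion beyond confinement by interpolation.

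Finally, Protocol 3.6.3 links dropout to study length, which points to later losses, where the effect is small. In the base case it is below 2 points from Day 70 on. That objection stands too.

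**Conclusion.** The concern holds in a limited form. As planned, a withdrawal before an ending criterion puts a truncated recovery into the summary statistics of a primary-objective endpoint, and relative to full follow-up of the same people the mean can only fall.

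The size is conditional. It is zero with no withdrawals. In the base case one withdrawal among eight costs about 3 to 8 points up to Day 56 and under 2 from Day 70. If completers run to Day 206, Day 70 costs 2.2. These figures rest on an assumed plateau, on a parent-drug half-life applied to excretion, and on how criterion 1 is counted. The documents supply no dropout rate or timing.

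Two stronger inferences are not supported. Mean recovery is not shown to be biased in this trial, because that requires a withdrawal nobody can yet assume. Nor is the completer mean the correct answer, or the two summaries certain to bracket it: the fast-excreter example fails to. No test depends on the figure, so this is a change worth making before database lock, not a flaw in the design.

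**What to change.** In SAP 16.2.4 and Table 14.2.2.4:

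1. Keep the PK-set summary of Ae_total and fe_total as planned.
2. Add beside it a prespecified supportive summary restricted to participants whose collection ended under criterion 1, under criterion 2 or at Day 206, with n shown for each summary.
3. Mark early-termination participants, including any who were replaced, with their last collection day, in the table or in Listing 16.2.6.2. State that they stay in the PK-set summary and are absent from the supportive one.
4. State that intervals after withdrawal are missing, not zero, in the by-interval summaries.

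The cost is SAP wording and programming; no visit, sample or participant changes. If nobody withdraws, the two summaries coincide. The downside should be written into the SAP: the supportive summary has fewer participants, omits drug-related withdrawals (who are not replaced), and is selected on outcome, since fast excreters reach criterion 1 sooner while slow or low excreters have longer in which to leave. It may be biased in either direction, which is why it should support the PK-set figure and not replace it.
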